4. TREATMENT ALLOCATIONS

4.1. Surgical procedures

The principal investigator, who has training and experience in both laparoscopy and NOTES, will perform all surgical procedures. He is therefore not blinded. All vNOTES participants will be blinded by three superficial “mock” skin incisions similar to those routinely done with the laparoscopic technique. The wound bandages will be left in place until the day 7 postoperative control to be removed by the coordinating investigator who will state at that moment that the wound healing has left an almost invisible scar as expected. This procedure aims to blind the participants, personnel and outcome assessors. The practice of performing “mock” incisions should not be considered as unethical: it is a procedure that has already been used in some surgical trials to minimise performance and detection bias whenever a subjective outcome is measured (22). The decision to use “mock” surgery is based on the clinical equipoise regarding the balance between benefits and adverse events for the two interventions under comparison (23).

4.1.1 vNOTES adnexectomy

This is the surgical procedure done in the intervention arm of the NOTABLE trial.

Clindamycin vaginal cream is administered on admission of the study participant to the outpatient ward.

The patient is placed in lithotomy position in a vacuum mattress. The abdomen, the vulva and the vagina are disinfected with an alcoholic betadine solution and draped. A Foley catheter is inserted into the bladder.

Three superficial skin incisions are made, one deep in the umbilicus and one in the left and right iliac fossa lateral of the epigastric vessels, and in the suprapubic region. The small vertical intraumbilical skin incision is closed with a monocryl 3/0 intradermal suture. Wound bandages are applied to all three skin incisions.

A 2.5 cm posterior colpotomy is made using a cold knife. The pouch of Douglas is opened using cold scissors. A Gelpoint Mini (Applied Medical) is used as vNOTES port and is inserted into the pouch of Douglas. CO₂ is insufflated until a maximal intraperitoneal pressure of 15mmHg. An optic is inserted and the peritoneal cavity is inspected. The patient is now placed in Trendelenburg position. The small intestine is lifted out of the pelvis.

The ureter is identified, but not routinely dissected. It is only dissected if it cannot be identified transperitoneally. The proximal end of the Fallopian tube is coagulated at its origin into the uterus

using a reusable bipolar grasping forceps before being cut using cold scissors. The ovarian ligament is coagulated and cut. The infundibulopelvic ligament is coagulated and cut. The adnexa is resected. If necessary, the same procedure is repeated for the contralateral side. The peritoneal cavity is rinsed and haemostasis is checked.

Small and benign adnexa will be removed directly through the wound protector part of the NOTES port. Large adnexa or adnexa that are macroscopically suspicious, will be placed in an endobag (Memobag, Teleflex). The purse string of the endobag is pulled through the wound protector and the purse string is released. The content of the cyst is aspirated to reduce the volume of the adnexa. The endobag is now removed with the adnexa inside it. The vNOTES port is removed.

The colpotomy is closed using three interrupted figure-of-eight Vicryl 2/0 sutures. A vaginal plug (betadine gauze 10cmx5m) is placed to be removed after 3 hours together with the Foley catheter.

Antibiotic administration:

Cefazolin 2g and metronidazol 1.5g are administered IV during the procedure.

Analgesia at the recovery room and the nursing ward: The pain management for both groups was discussed with two senior staff members of the department of anaesthesiology of the hospital, who are co-investigators. The protocol will be standard for both comparison groups and is presented in appendix V.

The vaginal plug and the Foley catheter are removed 3 hours after the surgery. The bandages are left in place and not changed unless soaked by blood with a need to change. The personnel of the recovery room will be asked to replace bandages only for hygienic reasons and immediately to apply a new wound dressing without revealing any information to the participant or personnel on the outpatient or hospitalization ward.

The decision to discharge or to admit to hospital for the night will be based solely on the choice of the woman to return home the same day or stay overnight. The outcome assessor will report this decision in the patient record without consulting the results of the pain scoring or whether or not additional analgesics were administered. Every woman leaving the hospital will be given a standard list with instructions not to have intercourse during six weeks and not to work for a period of four weeks. Telephone numbers will be provided for contacting the staff members on call in case urgent medical care for treating any adverse event is needed. Cefazolin 2g is administered IV before discharge.

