The fascia is closed using a Vicryl-1 running suture. The umbilicus and the other incisions are disinfected with Betadine solution. The skin incisions are closed with a monocryl 3/0 intradermal

suture and steri-strips. The wound sites are covered with a standard bandage. A vaginal plug (betadine gauze 10 cm x 5 m) is placed to be removed after 3 hours together with the Foley catheter.

Antibiotic administration:

Cefazolin 2g and metronidazol 1.5g are administered IV during the procedure.

Analgesia at the recovery room and the nursing ward: The pain management for both groups was discussed with two senior staff member of the department of anaesthesiology of the hospital, who are co-investigators. The protocol will be standard for both comparison groups and is presented in appendix V.

The vaginal plug and the Foley catheter are removed 3 hours after the surgery. The bandages are left in place and not changed unless soaked by blood with a need to change. The personnel of the recovery room will be asked to replace bandages only for hygienic reasons and immediately to apply a new wound dressing without revealing any information to the participant or personnel on the day care unit or hospitalisation ward.

The decision to discharge or to admit to hospital for the night will be based solely on the choice of the woman to return home the same day or stay overnight. The outcome assessor will report this decision in the patient record without consulting the results of the pain scoring or whether or not additional analgesics were administered. Every woman leaving the hospital will be given a standard list with instructions not to have intercourse during six weeks and not to work for a period of four weeks. Telephone numbers will be provided for contacting the staff members on call in case urgent medical care for treating any adverse event is needed. Cefazolin 2g is administered IV before discharge.

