- Postoperative pain defined by the total use of analgesics during the first week following surgery as described in the standardized pain treatment protocol, as an ordinal outcome. The use of pain medication following surgery should be reported in the nursing file. At home the participants should note in their participant log book the name, dosage, route of administration of any analgesic drug that was taken from the moment they are at home until the assessment on day 7 irrespective of whether this was done on their own initiative or after consulting a family physician or any other medical specialist. The assessment of the total use of analgesics will be done on day 7 by the outcome assessor (the coordinating investigator), who is blinded for the intervention done by the principal investigator.
- Postoperative infection defined by lower abdominal pain with fever $> 38^{\circ}\text{C}$ and positive clinical signs or laboratory findings, detected during the first six weeks of surgery, as a dichotomous outcome.
- Per- or postoperative complications according to the Clavien- Dindo classification detected during the first six weeks of surgery, as a dichotomous outcome (Appendix III).
- Hospital readmission during the first six weeks of surgery, as a dichotomous outcome.
- Incidence and intensity of dyspareunia recorded by the participants at 3 and 6 months by self-reporting using a simple questionnaire and VAS scale, as a dichotomous and ordinal

outcome. A measurement of the prevalence and the intensity of dyspareunia will be done at baseline assessment.

- Sexual wellbeing at baseline, at 3 and 6 months by self-reporting the SSFS.
- Quality of life at baseline, at 3 and 6 months by self-reporting the EQ-5D-3L questionnaire.
- Duration of surgery measured as the time in minutes from the insertion of the bladder catheter to the end of vaginal/abdominal wound closure, as a continuous outcome.

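### The named blinded assessor uncovers wounds that are described differently by arm on day 7, so assessor blinding is not protected for the day 7 analgesic total or for later outcomes that this person judges

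*Protocol*

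**What the plan says.** Section 4.1 explains that women in the vNOTES arm receive mock skin incisions resembling the laparoscopic ones, and then: "The wound bandages will be left in place until the day 7 postoperative control to be removed by the coordinating investigator". At that moment the coordinating investigator is to tell the woman that her wounds have healed to a barely visible scar. The aim is stated directly: "This procedure aims to blind the participants, personnel and outcome assessors".

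Section 5.3 assigns an outcome to the same person at the same time point. "The assessment of the total use of analgesics will be done on day 7", and the person doing it is "the outcome assessor (the coordinating investigator), who is blinded for the intervention done by the principal investigator".

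On skin closure, section 4.1.1 (vNOTES) says: "The small vertical intraumbilical skin incision is closed with a monocryl 3/0 intradermal suture". It does not say how the other mock incisions are closed. Section 4.1.2 (LSC) closes the skin incisions, without singling out the umbilicus, with the same intradermal material and adds strips: "suture and steri-strips. The wound sites are covered with a standard bandage".

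**The concern.** The mock incisions exist only to support blinding. Section 4.1 justifies them by the need to limit performance and detection bias for subjective outcomes, and the women in the vNOTES arm accept extra skin wounds for that purpose. The blinding claim covers outcome assessors as well as participants (Summary; section 4.1), and section 5.3 relies on it for analgesic use.

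If the assessor can tell the arm once the bandages are off, anything that person records or judges afterwards is no longer a blinded assessment, although the protocol would let it be reported as one. Postoperative pain, infection, complications and dyspareunia are all named research questions in section 1.6, so the label matters for how those results are read.

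**Working it through.** No arithmetic settles this point. The check sets the relevant sections side by side.

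**Step 1. Is it the same person at the same visit?** Yes. Section 4.1 gives bandage removal at the day 7 control to the coordinating investigator. Section 5.3 has the analgesic assessment done on day 7 by the outcome assessor, identified as the coordinating investigator. Neither section says which comes first.

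**Step 2. Do the described wounds differ?**

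| Feature | vNOTES (4.1.1) | LSC (4.1.2) |
|---|---|---|
| Umbilical wound | Small, superficial, vertical; no length given | Starts small and vertical, then extended to at most 2.5 cm; fascia opened and sutured |
| Other sites listed | Left and right iliac fossa, and suprapubic | Left and right iliac fossa only |
| Skin closure | Suture described for the umbilicus only; other sites not mentioned | Suture plus steri-strips for the skin incisions |

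The vNOTES text also disagrees with itself on number. It announces three incisions, but besides the umbilicus it lists "one in the left and right iliac fossa lateral of the epigastric vessels, and in the suprapubic region". One wound per listed site gives 1 + 2 + 1 = 4.

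**Step 3. Does anything mask the person who removes the bandages?** No. The only day 7 measure is the remark about healing. It is addressed to the participant and cannot mask the speaker. Sections 4.1.1 and 4.1.2 themselves treat sight of the wound as informative: recovery-room staff who must change a soaked bandage are to re-dress at once and disclose nothing to the participant or ward staff. No equivalent precaution is set for day 7.

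**Step 4. Which outcomes fall on which side of bandage removal?** (Sections 5.1.1, 5.1.2 and 5.3; Appendix VII)

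- Before: primary outcome (end of surgery), duration of surgery, same-day discharge (evening of surgery), and pain scores of days 1 to 6. Pain is scored twice daily for 7 days, so 2 × 7 = 14 scores are scheduled and 2 × 6 = 12 of them precede day 7.
- Same day, order not stated: the analgesic total and the two day 7 pain scores. The morning score is taken after the night's rest and probably precedes the visit. The evening score is taken before going to bed and probably follows it.
- Mostly or wholly after: infection, complications and readmission to week 6; dyspareunia, SSFS and EQ-5D-3L at 3 and 6 months.

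**The case against.** A reader might infer that blinding is lost before the outcomes are recorded. The documents do not support that. The primary outcome, duration of surgery, same-day discharge and at least 12 of the 14 scheduled pain scores come before the bandages are removed.

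A reader might also infer that removing the bandages necessarily shows the arm, because only the umbilical mock incision is sutured in vNOTES. That turns silence into a statement: section 4.1.1 does not say that the other incisions are left unsutured or without strips. Section 4.1 calls the mock incisions similar to the laparoscopic ones, and 2.5 cm is a ceiling for the laparoscopic umbilical wound, with no length given for the mock one. The cues are described; whether they reveal the arm is an inference.

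Three further points limit the reach of the concern:

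- The analgesic total is compiled from entries that already exist: the nursing file in hospital and the participant's daily log of dose, tablets and time at home. This leaves the assessor limited room to influence it.
- Section 5.1.2 gives infection and complications to a physician without naming the coordinating investigator. Infection has a partly objective definition, and readmission is a factual event.
- The participant has the scripted reassurance and no comparison wound.

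All of this stands and narrows the point. It does not remove it. The protocol names one person as blinded, has that person uncover wounds described differently by arm, sets no order of tasks, and provides nothing to keep that person blinded. Calling the trial single-blinded (section 2.1) is no answer either, since the Summary and section 4.1 explicitly claim blinded outcome assessors.

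**Conclusion.** The concern holds in a limited form: assessor blinding is unprotected from bandage removal onwards, rather than shown to be lost.

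- The day 7 analgesic total is exposed if the bandages come off before it is settled.
- Infection and complications to week 6 are exposed if the coordinating investigator judges them, which the protocol leaves open.
- The day 7 evening pain score is exposed if the visit precedes it and the woman infers her arm. The 3- and 6-month self-reports are exposed on the same condition that she infers it.

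The primary outcome, and so the non-inferiority conclusion, is unaffected, as are duration of surgery, same-day discharge and the pain scores of days 1 to 6. The size of any bias cannot be derived from the protocol. The conclusion assumes that the incisions are made and closed as described, and that the differences in the table can be seen at day 7. The change is worth making because it is cheap and protects a claim that the protocol relies on for subjective outcomes.

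**What to change.** 1. In sections 4.1 and 5.3, fix the order of the day 7 visit: review the log book and sign off the analgesic total before any bandage is touched. If the day 7 evening pain entry is made after the visit, keep it on a separate page and label it as recorded after bandage removal.
2. Have an existing staff member with no outcome-assessment role remove the bandages. This should not be the operating surgeon: that would put someone who knows the allocation in contact with the participant while self-reports are still outstanding.
3. Reconcile sections 4.1, 4.1.1 and 4.1.2 on the number, sites, closure and dressing of the mock and real incisions, so that the descriptions agree with the stated similarity. Which description is right is for the investigators to settle.
4. Name who assesses infection and complications to week 6, and claim assessor blinding only for outcomes recorded before bandage removal or by someone who has not seen the wounds.

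The cost is a small change to visit logistics with staff already in the trial, and fewer outcomes that can be described as blinded. Steps 1 and 2 do not protect the 3- and 6-month self-reports, because the woman sees her own wounds whoever uncovers them. Only step 3 bears on those.

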4.1.2 LSC adnexectomy

This is the surgical procedure done in the control arm of the NOTABLE trial.

Clindamycin vaginal cream is administered on admission of the study participant to the outpatient ward.

The woman is placed in lithotomy position in a vacuum mattress. The abdomen, the vulva and the vagina are disinfected with an alcoholic betadine solution and draped. A Foley catheter is inserted into the bladder.

A small vertical intra-umbilical skin incision is made. A Verress needle is inserted into the peritoneal cavity; the correct position of the needle tip is checked with Semm test. CO₂ is insufflated until a maximal intraperitoneal pressure of 15mmHg. The Verress needle is removed and replaced by a 10mm reusable trocar. An optic is inserted through the 10mm trocar and the peritoneal cavity is inspected. The patient is now placed in Trendelenburg position. Two reusable 5mm trocars are placed under direct vision in the left and right iliac fossa lateral of the epigastric vessels. The small intestine is lifted out of the pelvis.

The ureter is identified, but not routinely dissected. It is only dissected if it cannot be identified transperitoneally. The proximal end of the Fallopian tube is coagulated at its origin into the uterus using a reusable bipolar grasper and cut using cold scissors. The ovarian ligament is coagulated and cut. The infundibulopelvic ligament is coagulated and cut. The adnexa are resected and placed in an endobag (Memobag, Teleflex). If necessary, the same procedure is repeated for the contralateral side.

The peritoneal cavity is rinsed and haemostasis is checked. No drains are left in the peritoneal cavity except when there might be any uncertainty concerning the haemostasis. The 5 mm trocars are removed under direct vision. The purse string of the endobag is pulled through the 10 mm trocar upon removal of the optic. The umbilical incision is extended vertically in caudal direction, the size being not more than 2.5 cm. The fascia and peritoneum are opened and the proximal end of the endobag is pulled through the incision without causing any rupture if possible. If not possible, the endobag should be opened and the content of the cyst should be aspirated to reduce the volume of the adnexa. The aspirated fluid should be send for cytological examination. The endobag is now removed with the adnexa inside it.

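### Section 4.1.1 states three mock incisions but lists four sites, and the suprapubic one has no counterpart in the laparoscopic arm

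*Protocol*

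**What the plan says.** Section 4.1 introduces the mock wounds for vNOTES participants. It puts their number at three and describes them as "skin incisions similar to those routinely done with the laparoscopic technique". Their purpose is explicit: "This procedure aims to blind the participants, personnel and outcome assessors". The dressings are to be "left in place until the day 7 postoperative control to be removed by the coordinating investigator".

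Section 4.1.1 is the operative instruction. It opens with "Three superficial skin incisions are made, one deep in the umbilicus" and continues with "one in the left and right iliac fossa lateral of the epigastric vessels, and in the suprapubic region". It ends with "Wound bandages are applied to all three skin incisions".

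Section 4.1.2 describes the laparoscopic arm port by port. It starts at the umbilicus ("A small vertical intra-umbilical skin incision is made") and adds two 5 mm trocars, one in each iliac fossa. It mentions no suprapubic incision or trocar.

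**The concern.** The sentence that tells the surgeon where to cut disagrees with its own count and with the operation it is meant to imitate. A mock wound blinds only if it sits where a real wound would sit. A dressing over the pubis that only vNOTES patients carry would mark the arm for anyone who sees patients from both groups.

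Two groups could see it. Ward staff care for the women while the dressings are on. The coordinating investigator takes the dressings off at day 7 and, under Section 5.3, is also the blinded assessor of total analgesic use on that day. The outcomes within reach are therefore secondary ones recorded or handled by people who are supposed to be blinded.

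**Working it through.** No formula applies; the check is a count of sites.

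**Inputs**
- Stated number of mock incisions: 3, given once in Section 4.1 and once in Section 4.1.1.
- Stated number of bandaged incisions: 3, in Section 4.1.1.
- Mock sites named: Section 4.1.1.
- Laparoscopic sites named: Section 4.1.2.
- Planned size: 66 women, Section 6.1.

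**Count by site**

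| Site | Mock (4.1.1) | Laparoscopy (4.1.2) |
|---|---|---|
| Umbilicus | 1 | 1 |
| Left iliac fossa | 1 | 1 |
| Right iliac fossa | 1 | 1 |
| Suprapubic region | 1 | 0 |
| Total | 4 | 3 |

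The protocol's figure of 3 is not reproduced by its own list: 1 + 1 + 1 + 1 = 4. The surplus is 4 − 3 = 1 site, and that site is the one absent from laparoscopy.

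**Can any reading reconcile the three statements?**
- *The count governs and the suprapubic site is ignored.* Count and comparator agree, but the list is not followed.
- *The list governs.* Four wounds are made, which breaks the count of incisions, the count of bandages and the match to laparoscopy.
- *The two iliac fossae are taken as one incision.* The total becomes 3, but one cut cannot plausibly serve both sides of the abdomen, and the suprapubic wound still has no laparoscopic counterpart.

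Each reading breaks at least one statement.

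**Women exposed**
- If the list is followed: 66 / 2 = 33 (equal arms assumed).
- If three matching incisions are made: 0.

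**After correction.** With the suprapubic site removed, Section 4.1.1 names 1 + 1 + 1 = 3 sites. That equals the stated count, the number of bandages and the laparoscopic sites.

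**The case against.** The best reply is that the document already shows which reading is meant. Three is stated three times, Section 4.1 makes resemblance to laparoscopy the governing rule, and Section 4.1.2 leaves no doubt about the laparoscopic sites. One surgeon performs every operation, so different operators cannot read the line differently. Only the last words of the site list conflict, and they look like a leftover.

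Harm would also need a chain of events: the surgeon follows those words against everything else, blinded staff recognise the extra dressing as specific to one arm, and that knowledge shifts an outcome. The document supports none of these steps. The primary outcome is recorded at the end of surgery (Section 5.1.2). Same-day discharge rests on the woman's own choice. Pain scores and home analgesics are recorded by the participant, and the day-7 analgesic total is drawn from the nursing file and her log book, which leaves the assessor limited room for judgement.

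All of this stands, and it is why the point is minor. It does not remove the contradiction: someone auditing or repeating the mock procedure cannot tell from Section 4.1.1 alone which wounds are required.

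A reader might go further in two ways that the document does not support.
- One might infer that participants would identify their own arm. A woman sees only her own wounds, and nothing suggests that she would know a suprapubic dressing to be unusual.
- One might add that wound closure differs between the arms, since "The small vertical intraumbilical skin incision is closed with a monocryl 3/0 intradermal suture" is all that Section 4.1.1 says about closing the mock wounds. That is a separate question from number and location, and for the two lateral wounds it would rest only on silence.

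**Conclusion.** The contradiction is real, and its severity is minor. Section 4.1.1 lists one site more than it counts, and the extra site has no match in Section 4.1.2. The surplus exposes about 33 of 66 women if the list is followed and none if three matching incisions are made; the second is the more likely practice. The figure of 33 assumes equal arms.

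The primary outcome, sample size and analysis are unaffected. A reader might infer that blinding fails or that the secondary outcomes are biased. Neither follows: the document does not show that a fourth incision would be made, and the size of any effect on secondary outcomes cannot be derived from it.

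**What to change.** In Section 4.1.1, delete the closing reference to the suprapubic region, so that the mock sites are the umbilicus, the left iliac fossa and the right iliac fossa, as in Section 4.1.2. The counts of incisions and bandages can then stay as written. Check that the theatre instructions name the same three sites.

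The cost is a one-line protocol correction and that check. Sample size, visits and analysis do not change.

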5.2. Primary clinical outcome measure

The proportion of women successfully treated by removing the adnexal mass without spill, using a dichotomous outcome measure, will be used as a measure of efficacy. An important consideration in adnexal mass surgery is the inadvertent opening of the ovarian capsule. The likelihood of cyst rupture during removal by laparotomy or laparoscopy ranges from 10.5% to 41.8% in published studies (15). We will consider any spontaneous rupture of the cyst or any need to aspirate the cyst to allow removal from the abdominal cavity as treatment failures, even if the content of the ruptured cyst does not spill freely inside the cavity but remains within the endobag. By avoiding any subjective interpretations this rigorous definition allows an objective measure of success. As the risk of rupture may be associated to the cyst size, due to the stratified random sequence generation we anticipate that the risk of rupture due to the cyst size rather than the technique used will be symmetrically applicable.

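### Sections 4.1.1 and 4.1.2 set different aspiration rules for bagged masses, and because aspiration for removal is a primary failure, some masses that could come out intact may fail by instruction under vNOTES only

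*Protocol*

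**What the plan says.** **vNOTES (Section 4.1.1).** The specimen leaves through the vagina: "A 2.5 cm posterior colpotomy is made using a cold knife". Specimens are sorted before bagging: "Small and benign adnexa will be removed directly through the wound protector part of the NOTES port", whereas "Large adnexa or adnexa that are macroscopically suspicious, will be placed in an endobag". No size cut-off is given for large. For the bagged group the next instruction is "The content of the cyst is aspirated to reduce the volume of the adnexa", with no 'if needed' and no attempt at intact extraction first.

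**Laparoscopy (Section 4.1.2).** Every specimen is bagged. The opening is comparable: "The umbilical incision is extended vertically in caudal direction, the size being not more than 2.5 cm". The bag is to be drawn through without rupture where that can be done. Aspiration is the fallback: "If not possible, the endobag should be opened and the content of the cyst should be aspirated to reduce the volume of the adnexa".

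**Primary endpoint (Section 5.2).** In both arms the protocol counts "any spontaneous rupture of the cyst or any need to aspirate the cyst to allow removal from the abdominal cavity as treatment failures", including when the content stays inside the bag. It adds: "By avoiding any subjective interpretations this rigorous definition allows an objective measure of success".

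**Related text.** Section 3.2 excludes solid masses and masses highly suspicious for malignancy, but does not exclude large cysts. Section 4.1 has the principal investigator, who is not blinded, perform all operations. Section 6.1 assumes 95% success in both arms, a 15-point margin and 66 women in total.

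**The concern.** The step that decides success or failure follows a different written rule in each arm. Take a bagged mass that could be drawn out whole. Under laparoscopy it is tried, comes out, and is a success. Under vNOTES the text says to aspirate it, and if that aspiration is scored under Section 5.2 it is a failure. Part of the difference between arms would then reflect the wording of Section 4.1.1 and not the technique.

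Stratifying by cyst diameter does not help, because the rule differs by arm within each stratum. Section 5.2 relies on stratification to balance the risk of rupture due to size; it cannot balance an instruction given to one arm only.

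At stake is the interpretation of the primary comparison. The expected number of failures is small (5% of 33 is 1.65 women per arm), so one or two failures created by instruction matter.

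**Working it through.** **1. The two rules side by side**

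| Specimen | vNOTES (4.1.1) | Laparoscopy (4.1.2) |
|---|---|---|
| Small and benign | Removed directly, no bag, no aspiration step | Bagged, drawn out intact if possible |
| Large, cannot come out whole | Bagged, aspirated | Bagged, attempt fails, aspirated |
| Large or borderline, could come out whole | Bagged, aspirated | Bagged, drawn out intact |
| Macroscopically suspicious, could come out whole | Bagged, aspirated | Bagged, drawn out intact |

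The rows for small benign masses and for masses that cannot come out whole agree across arms as to aspiration. The asymmetry lies only in the last two rows.

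**2. How Section 5.2 scores the last two rows**

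- If every aspiration done to get the mass out counts, these are failures under vNOTES and successes under laparoscopy. The bias runs against vNOTES.
- If the word 'need' is taken strictly, the unblinded surgeon may regard a planned vNOTES aspiration as not needed and record a success. Since intact extraction was never tried, this could also cover masses that would not have come out whole. A laparoscopic aspiration follows a failed attempt, so it is always a failure. The bias then favours vNOTES.

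**3. The plan's own sample size**

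n per arm = 2 × 0.95 × 0.05 × (z₁₋α + z₀.₈₀)² / 0.15².

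- One-sided α = 0.05: 0.095 × (1.645 + 0.842)² / 0.0225 = 26.1, so 27 per arm and 54 in total. This reproduces Section 6.1.
- One-sided α = 0.025 gives 33.1, so 34 per arm and 68 in total. This does not reproduce it.
- Dropout: 54 / 0.85 = 63.5, so 64, as stated. The final target is 66, or 33 per arm.

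**4. Shift per affected woman (first reading of 'need')**

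One vNOTES woman aspirated by instruction whose mass would have come out intact moves the difference by 1/33 = 3.0 points. Five such women move it by 5/33 = 15.2 points, more than the margin.

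**5. Illustration of power (first reading of 'need')**

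Let b be the share of vNOTES women so affected. The documents give no value for b, so the values below are assumptions. Laparoscopy succeeds in 0.95 and vNOTES in 0.95 − b, with 33 per arm. The two-sided 95% interval of Section 6.3 gives 1.96. The interval method is not named in the protocol; the Wald interval is assumed.

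Power = Φ( (0.15 − b) / √{[0.95 × 0.05 + (0.95 − b)(0.05 + b)] / 33} − 1.96 )

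| b | Standard error | Power (formula) | Power (exact binomial, Wald limit) |
|---|---|---|---|
| 0 | 0.0537 | 80% | 81% |
| 1/33 | 0.0606 | 51% | 56% |
| 2/33 | 0.0665 | 27% | 33% |

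With 27 per arm and one-sided 5%, the same formula gives 81%, 56% and 33%, so the sensitivity does not hinge on the choice of α.

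**The case against.** The best defence is that vNOTES makes its size decision earlier. Laparoscopy bags everything, so it can only choose between intact removal and aspiration after bagging. vNOTES chooses before bagging, and the stated purpose of its aspiration is to reduce volume. Section 1.2 links aspiration to specimens too large for the existing incisions. If 'large' means not removable intact, both arms aspirate the same large masses and the gap for them goes towards zero. This stands as a plausible reading, but Section 4.1.1 does not state it, and it does not cover suspicious masses, which are bagged whatever their size. Those should be few, given the exclusion of high suspicion.

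A second defence is that Section 5.2 scores a need to aspirate, so a mass that could have come out whole is not clearly a failure. That is fair on the text, but it does not restore comparability. It hands the scoring to the unblinded operator and reverses the direction of the bias.

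Two stronger readings are tempting, and the documents support neither:

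- **That vNOTES success is capped at one minus the share of women bagged.** A reader might take this as the size of the problem. It counts masses that would be aspirated in either arm, so it does not measure the asymmetry.
- **That the bias is purely conservative, so a positive result is safe.** This holds only if every aspiration is scored as failure. Under the strict reading of 'need', a false conclusion of non-inferiority becomes easier.

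The case-series masses in Section 1.4.3 measured 35 to 110 mm, all wider than the 2.5 cm opening. Tissue stretches, so this does not show which masses would need aspiration.

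**Conclusion.** The point holds in a limited form and is a cheap improvement. As written, the extraction rule feeding the primary endpoint differs by arm, and for suspicious or borderline-large masses that could come out intact this may decide success or failure.

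The size is unknown. It may be near zero if 'large' is applied as not removable intact. What follows from the protocol's numbers is 3.0 points per affected woman against a 15-point margin. The fall in power from 80% to 51% and 27% is illustration only: it rests on assumed values of b, a Wald interval and the reading that every aspiration counts as failure.

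The direction is not fixed. If all aspirations count, the bias runs against vNOTES and costs power, and a failure to show non-inferiority could be wrongly put down to the technique. If planned aspirations are treated as not needed, the bias favours vNOTES and could support a false non-inferiority conclusion.

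**What to change.** - **Section 4.1.1:** adopt the rule of Section 4.1.2. Draw the bagged mass out intact if possible, and aspirate only if that is not possible. State that this also applies to macroscopically suspicious masses.
- **Section 5.2:** replace the criterion of a need to aspirate with what was done. Any rupture, or any aspiration performed before or during removal, is a failure in both arms.

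The cost is a few sentences of protocol text, with no change to sample size or data collection. The surgical team must agree one extraction rule for both routes. The unblinded surgeon will still judge when intact extraction has failed, so some subjectivity remains, but it would apply to both arms under the same rule. If the team already tries intact extraction under vNOTES, the edit only records practice.
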